#### **Concomitant Medications to be used with caution**

- Warfarin potassium (The effect of warfarin potassium may be enhanced.)
  - When other observation or tests suggested any abnormality, an international normalized ratio (INR), etc. should be measured to pay attention to changes in clotting ability, and the warfarin dose should be, as necessary, adjusted.
- Phenytoin (Phenytoin addiction may occur.)
  - The subject's condition should be monitored if they are on phenytoin. If any abnormality is noted, appropriate therapeutic measures such as a dose reduction and treatment discontinuation should be taken.
- For subjects assigned to Cohort 2:
  - Aminoglycoside antibiotics, vancomycin hydrochloride, and furosemide (concomitant administration of these drugs with cisplatin may enhance renal disorder and ototoxicity).

- Amphotericin B for injection (concomitant administration of the drug with cisplatin may enhance renal disorder).
- Piretanide (concomitant administration of the drug with cisplatin may enhance ototoxicity).

### 7.7.3 Rescue Medications and Supportive Care

#### 7.7.3.1 Supportive Care Guidelines for Pembrolizumab

Subjects should receive appropriate supportive care measures as deemed necessary by the treating investigator. Suggested supportive care measures for the management of adverse events with potential immunologic etiology are outlined below and in greater detail in the ECI guidance document. Where appropriate, these guidelines include the use of oral or intravenous treatment with corticosteroids as well as additional anti-inflammatory agents if symptoms do not improve with administration of corticosteroids. Note that several courses of steroid tapering may be necessary as symptoms may worsen when the steroid dose is decreased. For each disorder, attempts should be made to rule out other causes such as metastatic disease or bacterial or viral infection, which might require additional supportive care. The treatment guidelines are intended to be applied when the investigator determines the events to be related to pembrolizumab.

Note: if after the evaluation the event is determined not to be related, the investigator is instructed to follow the ECI reporting guidance but does not need to follow the treatment guidance (as outlined in the ECI guidance document). Refer to Section 5.2.1 for dose modification.

It may be necessary to perform conditional procedures such as bronchoscopy, endoscopy, or skin photography as part of evaluation of the event. Suggested conditional procedures, as appropriate, can be found in the ECI guidance document.

- **Pneumonitis:**
  - For **Grade 2 events**, treat with systemic corticosteroids. When symptoms improve to Grade 1 or less, steroid taper should be started and continued over no less than 4 weeks. See the guidelines shown in Table 5 for recurrent Grade 2 Pneumonitis.
  - For **Grade 3-4 events**, immediately treat with intravenous steroids. Administer additional anti-inflammatory measures, as needed.
  - Add prophylactic antibiotics for opportunistic infections in the case of prolonged steroid administration.

- **Diarrhea/Colitis:**

Subjects should be carefully monitored for signs and symptoms of enterocolitis (such as diarrhea, abdominal pain, blood or mucus in stool, with or without fever) and of bowel perforation (such as peritoneal signs and ileus).

- All subjects who experience diarrhea/colitis should be advised to drink liberal quantities of clear fluids. If sufficient oral fluid intake is not feasible, fluid and electrolytes should be substituted via IV infusion. For Grade 2 or higher diarrhea, consider GI consultation and endoscopy to confirm or rule out colitis.

- For **Grade 2 diarrhea/colitis** that persists greater than 3 days, administer oral corticosteroids.
- For **Grade 3 or 4 diarrhea/colitis** that persists > 1 week, treat with intravenous steroids followed by high dose oral steroids.
- When symptoms improve to Grade 1 or less, steroid taper should be started and continued over no less than 4 weeks.
- **Type 1 diabetes mellitus (if new onset, including diabetic ketoacidosis [DKA]) or  $\geq$  Grade 3 Hyperglycemia, if associated with ketosis (ketonuria) or metabolic acidosis (DKA)**
  - For **T1DM or Grade 3-4 Hyperglycemia**
    - Insulin replacement therapy is recommended for Type I diabetes mellitus and for Grade 3-4 hyperglycemia associated with metabolic acidosis or ketonuria.
    - Evaluate subjects with serum glucose and a metabolic panel, urine ketones, glycosylated hemoglobin, and C-peptide.
- **Hypophysitis:**
  - For **Grade 2** events, treat with corticosteroids. When symptoms improve to Grade 1 or less, steroid taper should be started and continued over no less than 4 weeks. Replacement of appropriate hormones may be required as the steroid dose is tapered.
  - For **Grade 3-4** events, treat with an initial dose of IV corticosteroids followed by oral corticosteroids. When symptoms improve to Grade 1 or less, steroid taper should be started and continued over no less than 4 weeks. Replacement of appropriate hormones may be required as the steroid dose is tapered.
- **Hyperthyroidism or Hypothyroidism:**

Thyroid disorders can occur at any time during treatment. Monitor subjects for changes in thyroid function (at the start of treatment, periodically during treatment, and as indicated based on clinical evaluation) and for clinical signs and symptoms of thyroid disorders.

  - **Grade 2** hyperthyroidism events (and **Grade 2-4** hypothyroidism):
    - In hyperthyroidism, non-selective beta-blockers (e.g. propranolol) are suggested as initial therapy.
    - In hypothyroidism, thyroid hormone replacement therapy, with levothyroxine or liothyronine, is indicated per standard of care.
  - **Grade 3-4** hyperthyroidism
    - Treat with an initial dose of IV corticosteroid followed by oral corticosteroids. When symptoms improve to Grade 1 or less, steroid taper should be started and continued over no less than 4 weeks. Replacement of appropriate hormones may be required as the steroid dose is tapered.

- **Hepatic:**
  - For **Grade 2** events, monitor liver function tests more frequently until returned to baseline values (consider weekly).
    - Treat with IV or oral corticosteroids
  - For **Grade 3-4** events, treat with intravenous corticosteroids for 24 to 48 hours.
  - When symptoms improve to Grade 1 or less, a steroid taper should be started and continued over no less than 4 weeks.
- **Renal Failure or Nephritis:**
  - For Grade 2 events, treat with corticosteroids.
  - For Grade 3-4 events, treat with systemic corticosteroids.
  - When symptoms improve to Grade 1 or less, steroid taper should be started and continued over no less than 4 weeks.
- **Management of Infusion Reactions:** Signs and symptoms usually develop during or shortly after drug infusion and generally resolve completely within 24 hours of completion of infusion. Table 6 shows treatment guidelines for subjects who experience an infusion reaction associated with administration of pembrolizumab (MK-3475).

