### 7.2.3 Dose modification and toxicity management for immune-related AEs associated with pembrolizumab

AEs associated with pembrolizumab exposure may represent an immunologic etiology. These immune-related AEs (irAEs) may occur shortly after the first dose or several months after the last dose of pembrolizumab treatment and may affect more than one body system simultaneously. Therefore, early recognition and initiation of treatment is critical to reduce complications. Based on existing clinical study data, most irAEs were reversible and could be managed with interruptions of pembrolizumab, administration of corticosteroids and/or other supportive care. For suspected irAEs, ensure adequate evaluation to confirm etiology or exclude other causes. Additional procedures or tests such as bronchoscopy, endoscopy, skin biopsy may be included as part of the evaluation. Based on the severity of irAEs, withhold or permanently discontinue pembrolizumab and administer corticosteroids. Dose modification and toxicity management guidelines for irAEs associated with pembrolizumab are provided in [Table 5](#).

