**Table 5 Dose modification and toxicity management guidelines for immune-related AEs associated with pembrolizumab**

General instructions: 1. Corticosteroid taper should be initiated upon AE improving to Grade 1 or less and continue to taper over at least 4 weeks. 2. For situations where pembrolizumab has been withheld, pembrolizumab can be resumed after AE has been reduced to Grade 1 or 0 and corticosteroid has been tapered. Pembrolizumab should be permanently discontinued if AE does not resolve within 12 weeks of last dose or corticosteroids cannot be reduced to $\leq 10$ mg prednisone or equivalent per day within 12 weeks. 3. For severe and life-threatening irAEs, IV corticosteroid should be initiated first followed by oral steroid. Other immunosuppressive treatment should be initiated if irAEs cannot be controlled by corticosteroids.				
Immune-related AEs	Toxicity grade or conditions (CTCAEv4.0)	Action taken to pembrolizumab	irAE management with corticosteroid and/or other therapies	Monitor and follow-up
Pneumonitis	Grade 2	Withhold	
 
Administer corticosteroids (initial dose of 1-2mg/kg prednisone or equivalent) followed by taper
 
	
 
Monitor participants for signs and symptoms of pneumonitis
 
Evaluate participants with suspected pneumonitis with radiographic imaging and initiate corticosteroid treatment
 
Add prophylactic antibiotics for opportunistic infections
 

	Grade 3 or 4, or recurrent grade 2	Permanently discontinue		
Diarrhea / colitis	Grade 2 or 3	Withhold	
 
Administer corticosteroids (initial dose of 1-2mg/kg prednisone or equivalent) followed by taper
 
	
 
Monitor participants for signs and symptoms of enterocolitis (ie, diarrhea, abdominal pain, blood or mucus in stool with or without fever) and of bowel perforation (ie, peritoneal signs and ileus).
 
Participants with <math>\geq</math> Grade 2 diarrhea suspecting colitis should consider GI consultation and performing endoscopy to rule out colitis.
 
Participants with diarrhea/colitis should be advised to drink liberal quantities of clear fluids. If sufficient oral fluid intake is not feasible, fluid and electrolytes should be substituted via IV infusion.
 

	Grade 4	Permanently discontinue		

General instructions:				

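### For pembrolizumab-related Grade 3-4 diarrhea/colitis, Section 7.7.3.1 suggests steroids only after more than 1 week of persistence, while Table 5 and Section 7.2.3 set no such wait, and the protocol does not say which governs

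*Combined protocol and SAP*

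**What the plan says.** Two parts of the protocol tell sites when to give steroids for immune-related diarrhea/colitis.

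Section 7.7.3.1 (Supportive Care Guidelines for Pembrolizumab) has two graded bullets. The one for the severe grades, 3 and 4, reads in its operative part "that persists > 1 week, treat with intravenous steroids followed by high dose oral steroids". The milder bullet, covering Grade 2 only, has a shorter condition and a different route: "that persists greater than 3 days, administer oral corticosteroids". The section describes its own status: "Suggested supportive care measures for the management of adverse events with potential immunologic etiology are outlined below", with more detail in a separate ECI guidance document. It also limits its scope: "The treatment guidelines are intended to be applied when the investigator determines the events to be related to pembrolizumab".

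Table 5 in Section 7.2.3 handles the same event by withholding pembrolizumab at Grade 2 or 3 and permanently discontinuing it at Grade 4. Its steroid instruction is "Administer corticosteroids (initial dose of 1-2mg/kg prednisone or equivalent) followed by taper". The third general instruction above the rows starts severe and life-threatening immune-related events on intravenous corticosteroids, followed by oral. The text of Section 7.2.3 bases steroid use on severity and states that "early recognition and initiation of treatment is critical to reduce complications".

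**The concern.** For a single severe event, the protocol suggests two different triggers. One is grade alone. The other is grade plus more than a week of persistence. A site that works from the Grade 3-4 bullet of Section 7.7.3.1 as written could hold back intravenous steroids in a severe colitis that the investigator has already judged related to pembrolizumab. A site that works from Table 5 has no such condition to meet.

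The persistence conditions also run the wrong way: the more severe grades carry the longer one. Appendix 4 describes Grade 4 events as life-threatening and needing urgent intervention, which sits badly with a condition of more than a week.

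What is at stake is participant safety and uniform toxicity care across sites. Section 5.4.2 says that there are no earlier safety data for pembrolizumab with oxaliplatin, and Section 4 makes adverse events and discontinuations due to them a secondary endpoint.

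**Working it through.** The plan gives no figure to reproduce. The check compares the texts.

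**Step 1. Triggers side by side.**

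| Item | Section 7.7.3.1 | Table 5 and Section 7.2.3 |
|---|---|---|
| Grade 2 | Oral steroids after more than 3 days | 1-2 mg/kg prednisone or equivalent, no persistence condition |
| Grade 3-4 | IV then high-dose oral, after more than 1 week | Same dose entry; IV first, then oral, for severe and life-threatening events; no persistence condition |
| Basis for steroids | Grade and duration | Severity; early start called critical |

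The Table 5 steroid instruction appears once for the diarrhea/colitis entry, and I read it as covering Grades 2 to 4. If it covered only Grades 2 and 3, the third general instruction would still reach Grade 4. Appendix 4 labels Grade 3 as severe (or medically significant) and Grade 4 as life-threatening, so that instruction on its face covers both grades.

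**Step 2. Direction of the conditions.** The threshold is 7 days at Grade 3-4 and 3 days at Grade 2, so it is 7 - 3 = 4 days longer at the higher grades.

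**Step 3. Is this the pattern of the section?** Grade-specific steroid instructions in Section 7.7.3.1: pneumonitis 2, diarrhea/colitis 2, hypophysitis 2, hyperthyroidism 1, hepatic 2, renal 2. The total is 2 + 2 + 2 + 1 + 2 + 2 = 11 over 6 disorders. The 2 for diarrhea/colitis carry a persistence condition; the other 11 - 2 = 9 do not. For Grade 3-4 pneumonitis the instruction is to treat at once.

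**Step 4. Does the work-up explain the wait?** Both texts place the work-up from Grade 2. Section 7.7.3.1 asks sites to "consider GI consultation and endoscopy to confirm or rule out colitis". In Table 5, participants with at least "Grade 2 diarrhea suspecting colitis should consider GI consultation and performing endoscopy to rule out colitis". The texts agree on investigation; only Section 7.7.3.1 adds a number of days before steroids.

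**Step 5. Is there a rule of precedence?** I found none.
- The only reference to Table 5 in the diarrhea, endocrine, hepatic, renal and pneumonitis bullets of Section 7.7.3.1 concerns recurrent Grade 2 pneumonitis.
- Its dose-modification pointer goes to Section 5.2.1, which does not exist here; Section 5.2 is Number of Participants.
- The most-conservative rule in Section 7.2.2 covers dose adjustments, not the timing of steroids.

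**Step 6. Size of the delay.** This would be the start time under Section 7.7.3.1 minus the start time under Table 5. Table 5 states no start time, so the difference cannot be computed.

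**The case against.** The strongest reply is that the two texts can be followed together. Section 7.7.3.1 offers suggested measures as the treating investigator sees fit, and Table 5 is also a set of guidelines. A site that starts steroids early breaches neither. This stands, and it limits the point to conflicting guidance. A reader might infer that the protocol obliges sites to leave Grade 3-4 colitis untreated for a week; it does not.

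Second, persistence most naturally counts from the onset of diarrhea. Sites are told to look for other causes, including infection, before they attribute the event to pembrolizumab, so some or all of the days may pass during that work-up. This also stands: a full extra week after attribution is not what the text says. It does not remove the mismatch, because steroids for an event attributed on the second day would still be conditional on persistence beyond a week.

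Third, the days may be deliberate observation time. TS-1 also causes diarrhea and has its own dose rules for it in Table 9. For Grade 2 this is a defensible clinical choice, and the documents do not show that the 3-day condition is the mistake. For Grade 3-4 it is less persuasive: the section applies once the event is judged related to pembrolizumab, and separating causes does not explain a longer period at higher grades.

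Fourth, the ECI guidance document may settle the matter. It was not available. If it agrees with Table 5, the Grade 3-4 bullet still needs correcting; if it repeats the 1-week condition, the conflict is wider.

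**Conclusion.** The point holds for Grade 3-4 diarrhea/colitis. Section 7.7.3.1 makes its suggested steroids conditional on more than 1 week of persistence, while Table 5, its third general instruction and Section 7.2.3 tie steroids to severity without a wait. The protocol does not say which text governs. For Grade 2 there is the same difference between texts, but which trigger is right is a clinical decision for the sponsor.

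Confidence is high for the textual mismatch and does not extend to its clinical consequence. How many participants would be affected, and by how many days, cannot be derived from the documents. Progression from an untreated Grade 3 to a Grade 4 event, which would move pembrolizumab from withheld to permanently discontinued, is a possible path but only an inference.

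A reader might also infer that the efficacy results are at risk. Nothing here supports that: the ORR analysis, its confidence interval and the sample size are unaffected. The change should be made on safety grounds.

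**What to change.** 1. In Section 7.7.3.1, delete the more-than-1-week condition from the Grade 3-4 diarrhea/colitis bullet. Keep the intravenous-then-high-dose-oral route, which matches the third general instruction of Table 5, and add a pointer to Table 5 for dose and pembrolizumab action.
2. For Grade 2, ask the sponsor's clinical team to reconcile the more-than-3-days condition with Table 5 and to state one trigger in both places.
3. Check that the ECI guidance document says the same.

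The cost is a short wording amendment, any IRB/IEC approval required under Appendix 1, and a notice to sites. The clinical downside is that some participants whose diarrhea is later attributed to TS-1 could receive steroids earlier; the existing limit to events judged related to pembrolizumab reduces this. Data collection and analysis do not change.

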#### 7.7.3.2 Supportive Care Guidelines for Oxaliplatin/ Cisplatin

Prevention and/or treatment of nausea and vomiting should be managed with:

1. IV EMEND (fosaprepitant) 150 mg IV or oral EMEND (aprepitant) 3 day pack 125 mg day 1, 80 mg day 2, 80 mg day 3
2. Plus Aloxi (Palonosetron) 0.25 mg IV

Nausea may also be managed with:

1. Zofran (Ondansetron) 8 mg twice a day
2. Or Compazine (Prochlorperazine) 10 mg 3-4 times per day

Additionally, use of steroids for oxaliplatin/ cisplatin associated anti-emetic support is allowed and is to follow the NCCN guideline, the local guidelines or institutional guidelines.

Please refer to the product label or local standards of care for additional oxaliplatin/ cisplatin supportive measures.

#### 7.7.3.3 Supportive Care Guidelines for TS-1

Please refer to the product label or local standards of care for TS-1 supportive measures.

#### 7.7.4 Diet/Activity/Other Considerations

##### 7.7.4.1 Diet

Subjects should maintain a normal diet unless modifications are required to manage an AE such as diarrhea, nausea or vomiting.

#### 7.7.4.2 Contraception

MK-3475 may have adverse effects on a fetus in utero. Furthermore, it is not known if MK-3475 has transient adverse effects on the composition of sperm.

For this trial, male subjects will be considered to be of non-reproductive potential if they have azoospermia (whether due to having had a vasectomy or due to an underlying medical condition).

Female subjects will be considered of non-reproductive potential if they are either:

- She is postmenopausal (defined as at least 12 months with no menses without an alternative medical cause; in women < 45 years of age a high follicle stimulating hormone (FSH) level in the postmenopausal range may be used to confirm a postmenopausal state in women not using hormonal contraception or hormonal replacement therapy. In the absence of 12 months of amenorrhea, a single FSH measurement is insufficient.);
- She had a hysterectomy and/or bilateral oophorectomy, bilateral salpingectomy or bilateral tubal ligation/occlusion, at least 6 weeks prior to screening;
- She has a congenital or acquired condition that prevents childbearing.

Female and male subjects of reproductive potential must agree to avoid becoming pregnant or impregnating a partner, respectively, while receiving study drug and for 120 days after the last dose of study drug by complying with one of the following:

- practice abstinence† from heterosexual activity;
- use (or have their partner use) acceptable contraception during heterosexual activity.

Acceptable methods of contraception are‡:

- Single method (one of the following is acceptable):
  - intrauterine device (IUD)
  - vasectomy of a female subject's male partner
  - contraceptive rod implanted into the skin
- Combination method (requires use of two of the following):
  - diaphragm with spermicide (cannot be used in conjunction with cervical cap/spermicide)
  - cervical cap with spermicide (nulliparous women only)
  - contraceptive sponge (nulliparous women only)
  - male condom or female condom (cannot be used together)

- hormonal contraceptive: oral contraceptive pill (estrogen/progestin pill or progestin-only pill), contraceptive skin patch, vaginal contraceptive ring, or subcutaneous contraceptive injection

† Abstinence (relative to heterosexual activity) can be used as the sole method of contraception if it is consistently employed as the subject's preferred and usual lifestyle and if considered acceptable by local regulatory agencies and ERCs/IRBs. Periodic abstinence (e.g., calendar, ovulation, sympto-thermal, post-ovulation methods, etc.) and withdrawal are not acceptable methods of contraception.

‡ If a contraceptive method listed above is restricted by local regulations/guidelines, then it does not qualify as an acceptable method of contraception for subjects participating at sites in this country/region.

Subjects should be informed that taking the study medication may involve unknown risks to the fetus (unborn baby) if pregnancy were to occur during the study. In order to participate in the study subjects of childbearing potential must adhere to the contraception requirement (described above) from the day of study medication initiation (or 14 days prior to the initiation of study medication for oral contraception) throughout the study period up to 120 days after the last dose of trial therapy. If there is any question that a subject of childbearing potential will not reliably comply with the requirements for contraception, that subject should not be entered into the study.

#### **7.7.4.3 Use in Pregnancy**

If a subject inadvertently becomes pregnant while on treatment the subject will immediately be discontinued from trial treatment. The site will contact the subject at least monthly and document the subject's status until the pregnancy has been completed or terminated. The outcome of the pregnancy will be reported to the SPONSOR without delay and within 24 hours if the outcome is a SAE (e.g., death, abortion, congenital anomaly, or other disabling or life-threatening complication to the mother or newborn). The study investigator will make every effort to obtain permission to follow the outcome of the pregnancy and report the condition of the fetus or newborn to the SPONSOR.

